### **1.3. Rationale for the study**

Largely attributable to globalization, without a prophylactic vaccine against SARS-CoV-2, COVID-19 will persist as a pandemic threat [2]. The few published clinical trials support the need for further researching of the efficacy of receiving vaccines that will protect against SARS-CoV-2 infections [3].

This study is a phase IIb clinical trial to collect sufficient safety data to support the use of this candidate vaccine in HIV infected individuals.

Two doses of Ad5-nCoV at  $5 \times 10^{10}$ vp will be administered to adults of 18 years of age and older, living with HIV, on stable treatment.

The Adenovirus type 5 platform has been successfully used by CanSino Biologics in its licensed Ebola virus vaccine. Two phase I clinical trials in China and one phase II clinical trial in Sierra Leone of Recombinant Ebola Virus Disease Vaccine (Adenovirus Type 5 Vector, rAd5) were conducted. The safety data are summarized below.

Between December 2014 and January 2015, a randomized, double-blinded, placebo-controlled, phase I clinical trial of single dose rAd5 Ebola vaccine was conducted in Jiangsu Province, China, to evaluate the safety, tolerability and immunogenicity in healthy people aged between 18 to 60 years. The vaccine was well tolerated with an adverse event reported in over 60% of participants after their primary immunization, and 71% of participants after the booster dose 6 months later [6, 7]. Local adverse reactions were pain, induration, and redness, swelling and itching. Systemic adverse reactions were fever, headache, fatigue, vomiting, diarrhea, myalgia, joint pain, sore throat and cough [6, 7]. Between March and August of 2015, a randomized, single center, open-label phase I clinical trial of rAd5 Ebola vaccine was conducted in Zhejiang Province, China, to evaluate its safety and immunogenicity in healthy Africans in China [8]. The safety results showed that solicited local adverse reactions were pain, swelling, induration and redness, mucosal damage, itching and rash at the injection site [8]. From October 2015, a randomized, single center, double-blinded, placebo-controlled phase II clinical trial of rAd5 Ebola vaccine was conducted in Sierra Leone [9], to evaluate its safety and immunogenicity in healthy Africans. The safety results showed that solicited local adverse reactions were mainly pain [9]. For full study details, please see articles referenced. Most of the adverse reactions were mild and self-limited. The above results indicated that the strength and extent of adverse reactions are acceptable and the rAd5 Ebola vaccine in healthy adults is tolerable and safe.

Immunogenicity of the rAd5 Ebola vaccine was demonstrated in all of the reported studies [6-9]. Higher antibody titers were demonstrated in participants who had low or absent pre-existing antibodies against adenovirus type 5; however, a significant immune response also occurred in individuals with pre-existing antibodies. These differences diminished after a booster dose of the rAd5 Ebola vaccine at 6 months [6-9].

Phase I and Phase II studies of the Adenovirus type 5 platform expressing SARS-CoV-2 spike protein have now been completed and demonstrate good safety and immunogenicity. A phase III trial to test the efficacy of the Ad5-nCoV vaccine is underway. A phase IIb study in persons living with HIV is warranted.

In its original version, the protocol limited inclusion to "people living with HIV on stable treatment and virologically suppressed..." .

Likewise, the design was double-blind versus placebo in a 2:1 ratio.

The advancement of the national vaccination reduced the possibilities of access to the study under such design, for which this protocol amendment was proposed.

Volunteers initially included in the study will receive two doses of the vaccine and will continue their follow-up as established in the protocol.

## **2. STUDY OBJECTIVES**

### **2.1 Primary Objectives**

The primary objectives of the study are related to the safety and immunogenicity of the Ad5-nCoV in persons living with HIV.

There are four primary safety objectives.

1. Evaluate the incidence of solicited adverse reactions within 7 days after vaccination.
2. Evaluate the incidence of unsolicited adverse events within 28 days after vaccination.
3. Evaluate the HIV viral load 24 and 52 weeks after vaccination.
4. Evaluate the incidence of serious adverse events (SAE) and medically attended adverse events (MAE) within 52 weeks after vaccination in all participants.

The primary immunogenicity objectives are:

- Evaluate the seroconversion rate of S-RBD IgG antibody on Day 28, Day 84 and Week 24 and Week 52 after vaccination, measured by ELISA.
- Evaluate the immunogenicity of one versus two doses of the vaccine.

### **2.2 Secondary Objectives**

#### **2.2.2 Secondary Safety Objective:**

- Evaluate the incidence of a decrease in CD4+ cell count by  $\geq 20\%$  at 24 and 52 weeks after vaccination.
- Evaluate changes in the CD4/CD8 ratio at 24 and 52 weeks compared to the basal value.

#### **2.2.3 Secondary Immunogenicity Objectives:**

1. Evaluate the GMT of S-RBD IgG antibody on Day 28, Day 84 and Week 24 and Week 52 after vaccination, measured by ELISA.
2. Evaluate the GMI of S-RBD IgG antibody on Day 28, Day 84 and Week 24 and Week 52 after vaccination, measured by ELISA.
3. Evaluate the seroconversion rate of pseudo-virus neutralizing antibody on Day 28, Day 84 and Week 24 and Week 52 after vaccination.
4. Evaluate the GMT of pseudo-virus neutralizing antibody on Day 28, Day 84 and Week 24

and Week 52 after vaccination.

5. Evaluate the GMI of pseudo-virus neutralizing antibody on Day 28, Day 84 and Week 24 and Week 52 after vaccination.
6. Evaluate the positive rate and level of IFN- $\gamma$ , TNF, IL-4, IL-5, IL-13 stimulated by peptide pool of S protein on Day 28, Day 84 and Weeks 24 and Week 52 after vaccination, measured by intracellular cytokine staining (ICS) (in a subset of approximately 50 participants).

#### 2.2.4 Exploratory Objectives

1. To evaluate the efficacy of two doses of Ad5-nCoV in preventing virologically confirmed (PCR positive) COVID-19 disease occurring 14 days and 28 days to 52 weeks after vaccination, regardless of severity.
2. To evaluate the efficacy of two doses of Ad5-nCoV in preventing virologically (PCR) or serologically (four-fold increase in SARS-CoV-2 anti-N IgG from pre-immunization to post symptom, defined as Day 21-28 post illness blood test, or pre-symptom and post-symptom blood test) confirmed COVID-19 disease occurring 14 and 28 days to 52 weeks after vaccination, regardless of severity.
3. To evaluate the efficacy of two doses of Ad5-nCoV in preventing severe COVID-19 disease caused by SARS-CoV-2 infection from 14 and 28 days to 24 and 52 weeks after vaccination.

*Severe disease is defined as: 1) Clinical signs at rest indicative of severe systemic illness (respiratory rate  $\geq$  30 per minute, heart rate  $\geq$  125 per minute,  $SpO_2 \leq 93\%$  on room air at sea level or  $PaO_2/FiO_2 < 300$  mm Hg), 2) Respiratory failure (defined as needing high-flow oxygen, non-invasive ventilation, mechanical ventilation or ECMO), 3) Evidence of shock ( $SBP < 90$  mm Hg,  $DBP < 60$  mm Hg, or requiring vasopressors), 4) Significant acute renal, hepatic, or neurologic dysfunction, 5) Admission to an ICU.*

4. Evaluate the efficacy of two doses of Ad5-nCoV in preventing asymptomatic disease of COVID-19 (confirmed by N IgG antibody on week 52 after vaccination).
5. Evaluate the severity of COVID-19 cases among vaccine recipients (based on WHO or FDA criteria) as compared to the control group, to measure antibody-mediated disease enhancement (ADE).
6. Evaluate for any evidence of SARS-CoV-2 virus shedding in COVID-19 cases that occurred 28 days to 52 weeks after vaccination (detection of viral nucleic acid every 2 days after being confirmed).
7. Perform genotyping of SARS-CoV-2 virus isolates of COVID-19 cases that occurred 28 days to 52 weeks after vaccination.
8. Evaluate incidence of suspected but unconfirmed cases of COVID-19 (either because of negative or no tests).

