**Assessment of adverse events****Assessment of intensity**

The intensity of the following solicited AEs will be assessed as described:

The maximum intensity of local injection site redness/swelling will be scored as follows:

0: ≤ 20 mm

1: > 20 - ≤ 50 mm

2: > 50 - ≤ 100 mm

3: > 100 mm

The grade of fever will be scored as follows (oral temperatures\*):

1: ≥ 38.0°C (100.4°F) - ≤ 38.5°C (101.3°F)

2: > 38.5°C (101.3°F) - ≤ 39.0°C (102.2°F)

3: > 39.0°C (102.2°F) - ≤ 40.0°C (104°F)

4: > 40.0°C (104°F)

\*oral temperature=axillary temperature+0.2°C

The investigator will assess the maximum intensity that occurred over the duration of the event for all unsolicited AEs (including SAEs) recorded during the study. The assessment will be based on the investigator's clinical judgment.

The intensity should be assigned to one of the following categories:

- Grade 1 (mild) = An AE which is easily tolerated by the participant, causing minimal discomfort and not interfering with everyday activities.
- Grade 2 (moderate) = An AE which is sufficiently discomforting to interfere with normal everyday activities.
- Grade 3 (severe) = An AE which prevents normal, everyday activities
- Grade 4= An adverse event that is potentially life threatening.
- Grade 5=An AE which results in death.

An AE that is assessed as Grade 3 (severe) should not be confused with a SAE. Grade 3 is a category used for rating the intensity of an event; and both AEs and SAEs can be assessed as Grade 3. An event is defined as 'serious' when it meets one of the predefined outcomes.

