### 9.3.5 Analysis of exploratory endpoints

#### Exploratory endpoints

- Efficacy of two doses of Ad5-nCoV in preventing symptomatic disease of COVID-19 (confirmed by PCR) occurring 14 and 28 days to 52 weeks after vaccination, regardless of severity.
- Efficacy of two doses of Ad5-nCoV in preventing virologically (PCR) or serologically (four-fold increase in SARS-CoV-2 anti-N IgG from pre-immunization to post symptom, defined as Day 21-28 post illness blood test, or pre-symptom to post-symptom blood test) confirmed COVID-19 disease occurring 14 and 28 days to 52 weeks after vaccination, regardless of severity.
- Efficacy of two doses of Ad5-nCoV in preventing severe COVID-19 disease caused by SARS-CoV-2 infection from 14 and 28 days to 24 and 52 weeks after vaccination.
- Efficacy of two doses of Ad5-nCoV in preventing asymptomatic disease of COVID-19 (confirmed by N IgG antibody on week 52 after vaccination).
- Severity of COVID-19 cases among vaccine recipients (based on WHO or FDA criteria) as compared to the control group, to measure antibody-mediated disease enhancement (ADE).
- SARS-CoV-2 virus shedding in COVID-19 cases that occurred 28 days to 52 weeks after vaccination (detection of viral nucleic acid every 2 days after being confirmed).
- Genotype of SARS-CoV-2 virus isolates of COVID-19 cases that occurred 28 days to 52 weeks after vaccination.
- Suspected but unconfirmed cases of COVID-19 (either because of negative or no tests).
- Evaluate incidence of suspected but unconfirmed cases of COVID-19 (either because of negative or no tests).

Analysis of endpoints will be descriptive. PCR confirmed positive subjects will be classified as having severe or non-severe disease. Severity of disease, SARS-CoV-2 virus shedding and Genotypes SARS-CoV-2 virus isolates will be listed by subject and date, along with demographic data, including the study centre. Suspected but unconfirmed cases and asymptomatic cases will also be listed.

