## **12.2 Endpoint Review Committee**

The Endpoint Review Committee (ERC) will be blinded to the treatment assignments. Each endpoint case will be reviewed independently by two ERC members to confirm endpoint and severity; if their adjudications conflict, the endpoint will also be reviewed by a third member and the endpoint will be adjudicated by the majority vote. Members of the ERC will be appointed by the Study Steering Committee. Each positive laboratory result will be reviewed by the ERC. A detailed outline of ERC regulations and endpoint case criteria, in addition to the criteria defined below, will be available in the ERC charter.

Endpoints cases are defined by any of the following events:

1. A participant has an illness visit and virological confirmation (positive PCR test). PCR SARS-CoV-2 tests are permitted to be carried out at local study sites. Every effort will be made to verify positive PCR tests in a central reference laboratory.
2. A participant has an illness visit and serological confirmation of SARS-CoV-2. A positive serology test is defined by a four-fold rise or greater to N antibody titers in association with the illness.
3. A participant has illness visit and both virological and serological confirmation.
4. A participant who does not present with any symptoms (does not have any illness visits) but demonstrates seroconversion to the N antigen between the Injection and Week 52 visits.

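### The definition of severe COVID-19 under exploratory objective 3 leaves out death, so a COVID-19 death with none of its five items documented is non-severe as written

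*Protocol*

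**What the plan says.** The protocol attaches a definition of severe disease to exploratory objective 3, in the same form in the synopsis and in section 2.2.4. It has five numbered items: abnormal clinical signs at rest, respiratory failure, shock, organ dysfunction and intensive care. The list closes with "4) Significant acute renal, hepatic, or neurologic dysfunction, 5) Admission to an ICU".

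Section 9.3.5, and the synopsis text on the analysis of exploratory endpoints, put the definition to use: "PCR confirmed positive subjects will be classified as having severe or non-severe disease". The same section limits the ambition of the analysis: "Analysis of endpoints will be descriptive".

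Section 12.2 describes adjudication: "Each endpoint case will be reviewed independently by two ERC members to confirm endpoint and severity". It also points to a document that is not part of the protocol: "A detailed outline of ERC regulations and endpoint case criteria, in addition to the criteria defined below, will be available in the ERC charter".

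**The concern.** A binary severity label should put the worst outcome in the worse class. Here the list is closed, death is not on it, and there is no third class for fatal cases. A participant who spends a night in intensive care and recovers is severe. A participant who dies of COVID-19 before anyone records vital signs, respiratory support, shock, organ dysfunction or an intensive care stay is non-severe.

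Prevention of severe disease is a stated exploratory objective, and severe cases in a trial of about 500 people are likely to be few. One death in the wrong class would therefore be a conspicuous error in the severe-disease listing. This is not detail left for a statistical analysis plan: the protocol states the rule, and the rule as stated gives the wrong label.

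**Working it through.** No formula decides this point, so the check is to set the texts side by side.

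1. **Count the items.** There are five in the synopsis and five in section 2.2.4. None of the five names death in either place.

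2. **Ask whether a death meets an item by implication.**
   - Item 1 needs a respiratory rate, heart rate, oxygen saturation or PaO2/FiO2 value.
   - Item 2 is tied to a need for support: "Respiratory failure (defined as needing high-flow oxygen, non-invasive ventilation, mechanical ventilation or ECMO". Death alone does not state that need, although an adjudicator might infer it.
   - Item 3 needs a blood pressure or vasopressor use.
   - Item 4 needs evidence of renal, hepatic or neurologic dysfunction.
   - Item 5 needs an intensive care admission.

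   The list does not say whether one item is enough. Even on the generous reading that any one suffices, a death with nothing documented meets 0 of 5.

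3. **Look for a repair elsewhere in the protocol.** Death appears in the definition of a serious adverse event (section 7.1), in the intensity grades and the fatal outcome category (section 7.2), and in the suspension rule (section 11.1). None of these is linked to severe COVID-19. The case definitions in section 3.5 do not grade severity. The four endpoint events listed in section 12.2 concern how a case is confirmed, not how severe it is.

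4. **Apply the rule.** PCR-confirmed, 0 of 5 items met, two classes available: non-severe.

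5. **Illustrate the size.** The protocol gives no attack rate and no severe fraction, so both are assumed here: 10% of 500 participants become confirmed cases, and 4% to 10% of those are severe.
   - Confirmed cases: 0.10 × 500 = 50.
   - Severe cases: 0.04 × 50 = 2 to 0.10 × 50 = 5.
   - If the mislabelled death is one of those 2 to 5, the listing is short by 1/2 = 50% to 1/5 = 20%.
   - If it comes on top of them, the true total is 3 to 6, and the shortfall is 1/3 = 33% to 1/6 = 17%.

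   These figures assume that one such death occurs. The protocol gives nothing from which to estimate how likely that is.

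**The case against.** The strongest reply is that the scenario is unlikely to arise. Section 3.5 says that data for deciding whether a case is severe will be collected. Section 5.1 has the illness form updated when a case meets the severe definition and again when it resolves. Section 7.2 requires the investigator to review the records of any serious adverse event, and section 7.3 provides for available post-mortem findings to be passed on. Two ERC members judge severity independently, with a third if they disagree, and could decide in retrospect that respiratory support had been needed. The charter may already cover death. The analysis is descriptive, severity is listed participant by participant, and deaths are summarised among the serious adverse events, so a reader would see the death in any case.

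Most of this stands, and it makes the point minor. It does not remove the gap. Cases are referred for local care and followed by telephone while in isolation, so an unobserved death may leave nothing to collect. The protocol gives the ERC no severity criteria other than the five items. If the charter does count death as severe, the protocol's own definition still says otherwise.

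A reader might also infer two stronger points that the protocol does not support. The first is a contradiction with the adverse event scale, which ends at "Grade 5=An AE which results in death". That scale grades the intensity of adverse events in general, whereas the five-item list is a COVID-19 case definition. They are different instruments and need not agree. The second is harm to the watch for disease enhancement. Objective 5 reads "Evaluate the severity of COVID-19 cases among vaccine recipients (based on WHO or FDA criteria) as compared to the control group", so it relies on outside criteria that the protocol does not reproduce, not on this list. No effect on it can be shown.

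**Conclusion.** The gap is real and minor. As worded, the protocol classifies a PCR-confirmed COVID-19 death as non-severe when none of the five items is documented. The clear effect is on objective 3 and on the severe or non-severe classification in section 9.3.5.

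It would be too strong to say that such a misclassification will happen. That depends on an undocumented death occurring and on how the ERC and its charter, which is not shown, would treat it. The range of 17% to 50% is an illustration from assumed rates, not a forecast. No hypothesis test, sample size or primary result is affected.

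**What to change.** Add a sixth item to the definition in the synopsis and in section 2.2.4: death due to COVID-19, as attributed by the ERC. In section 9.3.5 and the matching synopsis text, state that such a case is severe whatever else was recorded. Put the same rule in the ERC charter.

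Keep the attribution step in every place. A rule that made every fatal confirmed case severe would also capture a death from an unrelated cause after a mild infection. While the text is open, it would help to say whether any one item is sufficient.

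The cost is one clause in the definition, one sentence in the analysis text, each in two places, and a matching line in the charter. Deaths are already collected as serious adverse events, so no new data or visits are needed and the sample size does not change.

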### 3. STUDY DESIGN

#### 3.1 Summary

This Phase IIb study is a multi-centre clinical trial; approximately 500 participants 18 years of age and older, living with HIV will be enrolled.

All participants will receive a single dose of the study vaccine (Ad5-nCoV) on First Injection Visit, and a second dose of Ad5-nCoV at Day 56 (Second Injection Visit) and will be followed to monitor vaccine candidate safety, immunogenicity (antibody response), and efficacy for a duration of 52 weeks. A subset of participants will also have cellular immunity measured after receiving the  $5 \times 10^{10}$  vp Ad5-nCoV vaccine ( $\geq 4 \times 10^{10}$  vp).

**Candidate Vaccine:** Ad5-nCoV

**Vaccination schedule:** **A double-dose schedule is used for all participants. The First dose at the Injection Visit when entering the study and the Second dose at Day-56 Visit post baseline vaccination (Second Injection Visit).**

**Data collection:** This clinical trial will use a single, designated Electronic Data Capture System (EDC) where participant electronic case report forms (eCRFs) will be recorded.

**Safety Precautions:** Safety precautions will be outlined in detail in this section, as well as Section 7.

Blinding

#### 3.2 Study Groups

A total of 500 participants will be enrolled to receive the vaccine. All participants will be monitored for solicited adverse events for 7 days, unsolicited adverse events for 28 days, SAEs and MAEs for the one year duration of the study, and antibody measurements at baseline, Day 28, Day 84, week 24, and week 52. A subset of 50 participants will have cellular immunity measured at those same intervals.

This protocol amendment provides for unblinding of participants who were entered into the study in the double-blind schedule. For participants who entered the double-blind schedule, the visit process will be as follows:

a) Sites will receive an unblinding list detailing participants who received placebo or study vaccine. Participants who received placebo will be invited to continue in the study under the

open-label study scheme and should make visits from V1.B (first vaccine) onwards, after signing the informed consent, completing visits on day 28 (V2.B), day 56 (second dose) (V3.B), day 84 (V4.B), week 24 (V5.B) and week 52 (V6.B). In this group of participants already enrolled, no antibody dosage collection will be performed at the V1B visit; the V1 values at study entry will be taken. The letter B is added to the visits to differentiate this group of participants who must reorganize the schedule of visits from the administration of the first dose of CoVID vaccine after the unblinding. The procedures for this group are detailed in Table 2.

b) Participants who, after the unblinding, are found to have received study vaccine at the initial visit, will complete the visits established by protocol together with the administration of dose 2 of the study (day 56) onwards, after signing the informed consent. In this group of participants there will be no changes in the nomenclature of the visits.

For both arms (placebo and study vaccine), efficacy contacts are restarted with the second injection visit.

